In this trial, the overall incidence of skin toxicity including rash, dermatitis, acneiform rash, palmar-plantar erythrodysesthesia syndrome, and erythema was 87% in patients treated with trametinib and 13% in chemotherapy-treated patients. Severe skin toxicity occurred in 12% of patients treated with trametinib. Skin toxicity requiring hospitalization occurred in 6% of patients treated with trametinib, most commonly for secondary infections of the skin requiring intravenous antibiotics or severe skin toxicity without secondary infection. In comparison, no patients treated with chemotherapy required hospitalization for severe skin toxicity or infections of the skin. The median time to onset of skin toxicity in patients treated with trametinib was 15 days (range: 1 to 221 days) and median time to resolution of skin toxicity was 48 days (range: 1 to 282 days). Reductions in the dose of trametinib were required in 12% and permanent discontinuation of trametinib was required in 1% of patients with skin toxicity. Monitor patients receiving trametinib for skin toxicities and for secondary infections.

Embryofetal Toxicity

Based on its mechanism of action, trametinib can cause fetal harm when administered to a pregnant woman. trametinib was embryotoxic and abortifacient in rabbits at doses greater than or equal to those resulting in exposures approximately 0.3 times the human exposure at the recommended clinical dose. If this drug is used during pregnancy, or if the patient becomes pregnant while taking this drug, the patient should be apprised of the potential hazard to a fetus.

Advise female patients of reproductive potential to use highly effective contraception during treatment with trametinib and for 4 months after treatment. Advise patients to contact their healthcare provider if they become pregnant, or if pregnancy is suspected, while taking trametinib.

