2 ELIGIBILITY ASSESSMENT AND ENROLLMENT

2.1 Eligibility Criteria

2.1.1 Inclusion Criteria

- Histopathological confirmation of:
 - biliary tract carcinoma (BTC)

OR

- carcinoma in the setting of clinical and radiological characteristics which, together with the pathology, are highly suggestive of a diagnosis of BTC

Note: The term BTC includes intra- or extra- hepatic cholangiocarcinoma (CCA), gallbladder cancer or ampullary cancer.

- The tumor must have KRAS mutation(s) of clinical significance, confirmed by NCI Laboratory of Pathology or by FDA approved test.
- Patients must have received or been intolerant of at least one line of chemotherapy.
- Patients must have at least 1 measurable lesion by RECIST version 1.1 (see section **6.3**)
- Patients must have disease that is not amenable to potentially curative resection, ablation or transplantation.
- Age \geq 18 years.
- Performance status (ECOG) 0-2 (see [Appendix A](#))
- If liver cirrhosis is present, patient must have a Child-Pugh score <7 (Class A) (Section [Appendix B](#))
- Patients must have adequate organ and marrow function as defined below:

ANC	$\geq 1,500/\text{mcL}$
platelets	$\geq 100,000/\text{mcL}$
hemoglobin	$\geq 9 \text{ g/dL}$
total bilirubin	If cirrhosis present: Part of Child Pugh requirement If no cirrhosis: bilirubin should be $\leq 1.5 \times \text{ULN}$
ALT or AST	$\leq 5 \times \text{ULN}$.
Creatinine OR Measured or calculated creatinine clearance (CrCl) (eGFR may also be used in place of CrCl) ^A	$< 1.5 \times$ institution upper limit of normal OR $\geq 30 \text{ mL/min}/1.73 \text{ m}^2$ for participant with creatinine levels $\geq 1.5 \times$ institutional ULN
ALT (SGPT)=alanine aminotransferase (serum glutamic pyruvic transaminase); AST (SGOT)=aspartate aminotransferase (serum glutamic oxaloacetic transaminase); GFR=glomerular filtration rate; ULN=upper limit of normal.	
^A Creatinine clearance (CrCl) or eGFR should be calculated per institutional standard.	

- Patients must have at least 1 focus of disease that is amenable to mandatory tumor biopsies and be willing to undergo this. Ideally, the biopsied lesion should not be one of the target measurable lesions, although this can be up to the discretion of the investigators.
- The study drugs are harmful for developing human fetus. For this reason, women of child-bearing potential and men must agree to use adequate contraception (hormonal or barrier

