method of birth control; abstinence) at the study entry, for the duration of study treatment and up to 4 months after the last dose of the study drug(s). Should a woman become pregnant or suspect she is pregnant while she or her partner is participating in this study, she should inform her treating physician immediately.

- Patients must be able to understand and be willing to sign a written informed consent.

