⁶ EKG must be performed at screening and on Day 1 of every cycle. Echocardiogram must be completed at screening, C2D1, and every 3 cycles thereafter (i.e. C5D1, C8D1, etc.) and as clinically indicated. Troponin I test and cardiology consult only if clinically indicated.

⁷ HIV, Hepatitis B and C serology. If screening serology results indicate potential HBV or HCV infection, viral load will be tested before starting investigational agents. TB testing will be performed only if clinically indicated.

⁸ Biochemical Profile: electrolytes, BUN, creatinine, AST, ALT, total and direct bilirubin, calcium, phosphorus, albumin, magnesium.

⁹ Pregnancy test for female participants of childbearing potential (serum or urine; if urine is positive it must be confirmed with serum test

Abbreviated Title: Trametinib and HCQ in BTC

Version Date: 04/06/2022

¹⁰ CT scan of chest, abdomen and pelvis (or MRI of chest, abdomen and pelvis if clinically indicated) every 8 (+/-1) weeks after start of study therapy. If patient taken off treatment for reason other than progression, CT scans will continue until progression or 5 months have passed since the start of study therapy whatever comes earlier. MRI of brain can be done at screening if clinically indicated.

¹¹ Mandatory tumor biopsies will be performed at baseline and any day during week 3 of cycle 2. If patient disease progresses before this, post-treatment biopsy might be performed per PI discretion at the time of progression.

¹² On Day 1 of cycles 1-4, then every 12 weeks until PD

¹³ +/- 1 week

¹⁴ After Safety Follow Up visit, subjects will be followed for adverse events by phone call or e-mail at 60 (+/- 14 days) and 90 (+/- 14 days) days. After that every 6 (\pm 1) months by phone call or e-mail for survival. If patient is taken off treatment for reason other than disease progression before 5 months have passed since the start of study therapy, we will continue to invite patient every 8 (+/-1) weeks for imaging studies until disease progression or 5 months have passed since the start of study therapy whatever comes earlier. Outside scans are acceptable.

¹⁵ If patients are not willing to come to the NIH Clinical Center, they may be followed by phone call or e-mail.

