3.6.1 Criteria for Removal from Protocol Therapy

- Participant requests to be withdrawn from active therapy
- Unacceptable toxicity (both drugs) as described in Section [3.3](#)
- PI discretion
- Positive pregnancy test or intent to become pregnant
- Drugs become unavailable
- Initiation of therapy that prevents further administration of study treatment
- Confirmed disease progression based on radiographic progression per RECIST 1.1.
- Permanent loss of capacity to consent, per requirements of section [12.3](#)

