In addition to evaluation of the proportion of patients that are progression-free at 5 months, the progression-free survival for patients will also be analyzed via a Kaplan-Meier curve. This curve will be compared informally to other published results in similar patients. As well, the overall response rate will be reported, and the overall survival will be reported using a Kaplan-Meier curve. It is anticipated that up to 10 patients per year will be able to enroll onto this protocol. Thus, it is expected that accrual of up to 17 total patients can be completed in approximately 2 years. In order to allow for a small number of unevaluable patients and screen failures, the accrual ceiling will be set at 30 patients.

To evaluate the response rate, proportion of patients obtaining CR and PR per RECIST 1.1 criteria of all evaluable patients will be analyzed.

To address safety, tolerability and feasibility of trametinib in combination with hydroxychloroquine, adverse events will be tabulated by grade according to CTCAE and analyzed and reported descriptively. The fraction of patients who experience a response will be reported along with confidence intervals.

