12.4.1.9 Other Risks

Risks include the possible occurrence of any of a range of side effects which are listed in the Consent Document or this protocol document. Frequent monitoring for adverse effects will help to minimize the risks associated with administration of the study agents.

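### The contraception rule in inclusion criterion 2.1.1 is worded below the level that Section 1.2.5.2 advises for women on trametinib

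*Combined protocol and SAP*

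**What the plan says.** Two places in the combined protocol and SAP set out contraception for participants.

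- Section 1.2.5.2 (Toxicity, under Embryofetal Toxicity) is background on trametinib addressed to those treating patients: "Advise female patients of reproductive potential to use highly effective contraception during treatment with trametinib and for 4 months after treatment".
- Section 2.1.1 (Inclusion Criteria) is the eligibility rule. It starts from the premise that the study drugs can injure a fetus and goes on: "For this reason, women of child-bearing potential and men must agree to use adequate contraception (hormonal or barrier". The sentence then continues: "method of birth control; abstinence) at the study entry, for the duration of study treatment and up to 4 months after the last dose". The criterion also tells a woman to inform her physician at once of a known or suspected pregnancy.

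Other provisions deal with pregnancy but not with contraceptive method. Section 2.1.2 excludes pregnant women. The Study Calendar in Section 3.4 schedules tests at screening and on Day 1 of every cycle, and footnote 9 specifies: "Pregnancy test for female participants of childbearing potential (serum or urine; if urine is positive it must be confirmed with serum test". Section 3.6.1 lists as a reason to stop therapy: "Positive pregnancy test or intent to become pregnant".

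**The concern.** Eligibility is checked against 2.1.1, not against the background section. As 2.1.1 is worded, a woman who relies on a barrier method alone, of any kind, meets it in full. Yet Section 1.2.5.2 says she should be advised to use something described in stronger terms.

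What is at stake is fetal exposure. Section 1.2.5.2 expects fetal harm from trametinib's mechanism of action. It also reports embryo toxicity and pregnancy loss in rabbits at exposures starting near 0.3 times the human exposure at the recommended dose. The outcome is serious, and the rule meant to prevent it should carry the level that the protocol itself recommends.

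**Working it through.** The plan gives no figure to reproduce on this point, so the check compares texts and adds a rough count.

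1. **Level.** 1.2.5.2 says *highly effective*; 2.1.1 says *adequate*. Neither term is defined anywhere in the document. In ordinary use the first is the stronger.
2. **Methods.** 2.1.1 offers hormonal, barrier or abstinence as alternatives. The barrier option has no qualifier: no double barrier, spermicide or second method. Any barrier method alone therefore satisfies the rule. 1.2.5.2 lists no methods.
3. **Duration.** Both texts give 4 months after treatment. 1.2.5.2 says *for* 4 months; 2.1.1 says *up to* 4 months, which read literally sets a maximum. The intent is probably the same, but only the first is a clear minimum.
4. **Status.** 1.2.5.2 is advice to be given; 2.1.1 is something the participant must agree to. Both can be followed together.
5. **Scope.** 2.1.1 is wider: it covers men, both study drugs and pregnancy notification. 1.2.5.2 covers women and trametinib only.
6. **Does another provision raise the level?** No. The pregnancy exclusion, the tests, the removal criterion and the notification duty exclude, detect or respond to a pregnancy. None sets a contraceptive standard.
7. **Is 1.2.5.2 elsewhere turned into operative rules?** Yes, in several places. Its ejection-fraction schedule reappears as the echocardiogram schedule in calendar footnote 6. Its permanent discontinuation for retinal vein occlusion and for interstitial lung disease reappears in Table 6. The 4-month period itself reappears in 2.1.1. The contraception level does not. Section 12.4.3 names the eligibility criteria among the means of minimizing risk and points to 1.2.5.2 for the adverse reactions.

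**Number of women.** The document gives no sex or age split. Purely as an assumption, let 5% to 20% of patients be women of child-bearing potential.

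- Trial stops at stage one (10 patients): 10 × 0.05 = 0.5 to 10 × 0.20 = 2.
- Both stages completed (17 patients): 17 × 0.05 = 0.85 to 17 × 0.20 = 3.4.
- Accrual ceiling (30 patients): 30 × 0.20 = 6 at most. This overstates the count of treated women, because Section 10.2 explains the ceiling thus: "In order to allow for a small number of unevaluable patients and screen failures, the accrual ceiling will be set at 30 patients". Screen failures receive no study drug.

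Women using a barrier method alone are an unknown subset of these, possibly none. The document gives no contraceptive failure rates, so no pregnancy risk can be calculated.

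**The case against.** The strongest reply is that a background section and an eligibility minimum do different jobs. Nothing in 2.1.1 prevents or weakens stronger counselling, and a minimum backed by fuller advice is a legitimate design choice. This stands as far as it goes. A reader might infer that the protocol contradicts itself; it does not. What remains is that the one level a participant is bound to is the lower of the two.

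The ranking is also open to challenge. The document does not say that a barrier method alone falls short of highly effective; that is ordinary meaning, not a protocol statement. The difference between the two adjectives, however, is on the page.

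The consent form was not available. Section 12.4.1.9 relies on it for risks: "Risks include the possible occurrence of any of a range of side effects which are listed in the Consent Document or this protocol document". Section 12.5 has an investigator explain the risks in person or remotely. A reader might infer that women are told less than 1.2.5.2 advises; the documents do not show that. The wording of 2.1.1 is a separate matter and is fully visible.

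A reader might also infer that after the last dose 2.1.1 is the only preventive measure. That is not supported, because the advice in 1.2.5.2 covers the same 4 months. Nor is this a point about pregnancy testing. The calendar marks no pregnancy test after treatment ends, but a change to the contraception wording would leave that as it is.

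Finally, the exclusion, the per-cycle tests, the removal rule and the wider scope of 2.1.1 do limit the consequences of a weaker method. They do not substitute for the advised level.

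**Conclusion.** The point holds as a wording mismatch on participant safety: the binding criterion is pitched below the protocol's own advice, in level and, read literally, in duration. It is minor and worth considering. It has no bearing on the two-stage design, error rates, sample size or analysis.

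The conclusion rests on two things: reading *adequate* as weaker than *highly effective* in ordinary usage, and the absence of any other provision in the available text that raises the level. The number of women affected is unknown and likely very small; the counts shown depend wholly on an assumed share. If the consent form already carries the stronger wording, the practical gap is smaller still, though 2.1.1 would remain out of step.

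**What to change.** In Section 2.1.1, for women of child-bearing potential:

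- replace adequate contraception with highly effective contraception, and state which methods are accepted;
- do not list an unqualified barrier method as sufficient on its own;
- replace up to 4 months with for at least 4 months after the last dose of the study drug(s).

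Keep the existing coverage of men, both drugs and pregnancy notification. Check that the consent form and other participant materials use the same wording.

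The cost is an amendment to one criterion, any matching participant text, and a slightly narrower choice of methods for a few women. No visits, tests or analyses are added.

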1.2.5.3 Clinical trial experience

Trametinib as a single agent was evaluated in 329 patients including 107 (33%) exposed for \geq 6 months and 30 (9%) exposed for \geq one year. Trametinib as a single agent was studied in open-label, single-arm trials (N = 118) and in an open-label, randomized, active-controlled trial (N = 211; the METRIC study, a randomized, open-label trial of patients with BRAF V600E or V600K mutation-positive unresectable or metastatic melanoma). The median age was 54 years, 60% were male, > 99% were White, and all patients had unresectable or metastatic melanoma. All patients received 2 mg once-daily doses of trametinib or chemotherapy (N = 99) (either dacarbazine 1,000 mg/m² every 3 weeks or paclitaxel 175 mg/m² every 3 weeks). Patients with abnormal LVEF, history of acute coronary syndrome within 6 months, or current evidence of Class II or greater

congestive heart failure (New York Heart Association) were excluded. The median duration of treatment with trametinib was 4.3 months.

In this study, 9% of patients receiving trametinib experienced adverse reactions resulting in permanent discontinuation of trial medication. The most frequent adverse reactions resulting in permanent discontinuation of trametinib were decreased left ventricular ejection fraction (LVEF), pneumonitis, renal failure, diarrhea, and rash. Adverse reactions led to dose reductions in 27% of patients treated with trametinib. Rash and decreased LVEF were the most frequent reasons cited for dose reductions of trametinib. **Table 1 and Table 2** present adverse reactions and laboratory abnormalities, respectively, of trametinib as a single agent in the METRIC study.

Table 1. Select Adverse Reactions Occurring in $\geq 10\%$ of Patients Receiving Trametinib and at a Higher Incidence ($\geq 5\%$) than in the Chemotherapy Arm or $\geq 2\%$ (Grades 3 or 4) Adverse Reactions in METRIC

Adverse Reactions	Trametinib N = 211		Chemotherapy N = 99	
	All Grades ^{a, b}	Grades 3 ^b and 4 ^{c, b}	All Grades ^a	Grades 3 and 4 ^{c, b}
Skin and subcutaneous tissue				
Rash	57	8	10	0
Acneiform dermatitis	19	<1	1	0
Dry skin	11	0	0	0
Pruritus	10	2	1	0
Paronychia	10	0	1	0
Gastrointestinal				
Diarrhea	43	0	16	2
Stomatitis ^d	15	2	2	0
Abdominal pain ^e	13	1	5	1
Vascular				
Lymphedema ^f	32	1	4	0
Hypertension	15	12	7	3
Hemorrhage ^g	13	<1	0	0

^aEvents included are higher in the trametinib arm compared with chemotherapy by $\geq 5\%$ in 141 overall incidence or by $\geq 2\%$ Grade 3-4 adverse reactions higher in trametinib arm compared 142 with chemotherapy.

^bNational Cancer Institute Common Terminology Criteria for Adverse Events, version 4.0.

^cGrade 4 adverse reactions were limited to rash (n = 1) in trametinib arm and diarrhea (n = 1) in the chemotherapy arm.

^dIncludes the following terms: stomatitis, aphthous stomatitis, mouth ulceration, and mucosal inflammation.

^eIncludes the following terms: abdominal pain, abdominal pain lower, abdominal pain upper, and abdominal tenderness.

^fIncludes the following terms: lymphedema, edema, and peripheral edema.

^gIncludes the following terms: epistaxis, gingival bleeding, hematochezia, rectal hemorrhage, melena, vaginal hemorrhage, hemorrhoidal hemorrhage, hematuria, and conjunctival hemorrhage.

Other clinically important adverse reactions observed in $\leq 10\%$ of patients (N = 329) receiving trametinib were: bradycardia, dry mouth, folliculitis, rash pustular, cellulitis, rhabdomyolysis, dizziness, dysgeusia, blurred vision, dry eye

Table 2. Laboratory Abnormalities Occurring at a Higher Incidence in Patients Treated with Trametinib in the METRIC Study [Between-arm Difference of $\geq 5\%$ (All Grades) or $\geq 2\%$ (Grades 3 or 4)^a]

Laboratory Abnormality	Trametinib N = 211		Chemotherapy N = 99	
	All Grades	Grades 3 and 4	All Grades	Grades 3 and 4
Increased aspartate aminotransferase (AST)	60	2	16	1
Hypoalbuminemia	42	2	23	1
Increased alanine aminotransferase (ALT)	39	3	20	3
Anemia	38	2	26	3
Increased alkaline phosphatase	24	2	18	3

^aOnly grade 3 adverse reactions were reported in either treatment arm

Further information on these risks (e.g. presenting symptoms) can be found in the current version of the trametinib package insert.

1.2.6 Hydroxychloroquine

1.2.6.1 Mechanism of Action

HCQ can inhibit lysosomal acidification and prevent the degradation of autophagosomes, thereby suppressing autophagy. The mechanism by which chloroquine derivatives interfere with autophagy is still not very well understood.

1.2.6.2 Toxicity

Ocular:

Irreversible retinal damage has been observed in some patients who had received HCQ sulfate. Significant risk factors for retinal damage include daily doses of HCQ sulfate greater than 6.5 mg/kg (5 mg/kg base) of actual body weight, durations of use greater than five years, subnormal glomerular filtration, use of some concomitant drug products such as tamoxifen citrate and concurrent macular disease. A baseline ocular examination is recommended within the first year of starting HCQ. The baseline exam should include best corrected distance visual acuity (BCVA), an automated threshold visual field (VF) of the central 10 degrees (with retesting if an abnormality is noted), and spectral domain ocular coherence tomography (SD-OCT). For individuals with significant risk factors (daily dose of HCQ sulfate greater than 5.0 mg/kg base of actual body weight, subnormal glomerular filtration use of tamoxifen citrate or concurrent macular disease) monitoring should include annual examinations which include BCVA, VF and SD-OCT.

For individuals without significant risk factors, annual exams can usually be deferred until five years of treatment. In individuals of Asian descent, retinal toxicity may first be noticed outside the macula. In patients of Asian descent, it is recommended that visual field testing be performed in the central 24 degrees instead of the central 10 degrees. It is recommended that HCQ be discontinued if ocular toxicity is suspected and the patient should be closely observed given that retinal changes (and visual disturbances) may progress even after cessation of therapy.

Cardiac Effects, including Cardiomyopathy and QT prolongation:

Abbreviated Title: Trametinib and HCQ in BTC

Version Date: 04/06/2022

Post marketing cases of life-threatening and fatal cardiomyopathy have been reported with use of HCQ as well as with use of chloroquine. Patients may present with atrioventricular block, pulmonary hypertension, sick sinus syndrome or with cardiac complications. ECG findings may include atrioventricular, right or left bundle branch block. Signs or symptoms of cardiac compromise have appeared during acute and chronic treatment. Clinical monitoring for signs and symptoms of cardiomyopathy is advised, including use of appropriate diagnostic tools such as ECG to monitor patients for cardiomyopathy during HCQ therapy. Chronic toxicity should be considered when conduction disorders (bundle branch block/atrio-ventricular heart block) or biventricular hypertrophy are diagnosed. If cardiotoxicity is suspected, prompt discontinuation of HCQ may prevent life-threatening complications. HCQ prolongs the QT interval. Ventricular arrhythmias and torsade's de pointes have been reported in patients taking HCQ. Therefore, HCQ should not be administered with other drugs that have the potential to prolong the QT interval

Worsening of psoriasis and porphyria:

Use of HCQ in patients with psoriasis may precipitate a severe attack of psoriasis. When used in patients with porphyria the condition may be exacerbated. The preparation should not be used in these conditions unless in the judgment of the physician the benefit to the patient outweighs the possible hazard.

Proximal Myopathy and Neuropathy:

Skeletal muscle myopathy or neuropathy leading to progressive weakness and atrophy of proximal muscle groups, depressed tendon reflexes, and abnormal nerve conduction, have been reported. Muscle and nerve biopsies have been associated with curvilinear bodies and muscle fiber atrophy with vacuolar changes. Assess muscle strength and deep tendon reflexes periodically in patients on long-term therapy with HCQ.

Neuropsychiatric events, including suicidality:

Suicidal behavior has been rarely reported in patients treated with HCQ.

Hypoglycemia:

HCQ has been shown to cause severe hypoglycemia including loss of consciousness that could be life threatening in patients treated with or without antidiabetic medications. Patients treated with HCQ should be warned about the risk of hypoglycemia and the associated clinical signs and symptoms. Patients presenting with clinical symptoms suggestive of hypoglycemia during treatment with HCQ should have their blood glucose checked and treatment reviewed as necessary.

